Protocol ID: 1708785351

ClinicalTrials.gov ID: NCT03435835

Date of document: 01/28/2022

Official Title: Heat Therapy to Reduce Leg Pain and Improve Walking Tolerance in Patients
With Symptomatic Peripheral Artery Disease

STUDY PROTOCOL AND STATISTICAL ANALYSIS PLAN

Experimental Design

A schematic of the experimental protocol is depicted in Figure 1. To familiarize participants with the symptom-limited cardiopulmonary treadmill exercise test and assess the test-retest reliability of walking tolerance, two tests were completed at baseline, at least 72 hours apart. On visit 1, participants underwent a lower extremity arterial examination to determine the ankle-brachial index (ABI). Next, participants were escorted to an adjacent room and underwent resting pulmonary function testing, followed by a graded cardiopulmonary treadmill exercise test. Pulmonary oxygen uptake ($\dot{V}O_2$) and calf muscle oxygenation were measured continuously throughout the test. Similar procedures were followed on visit 2, with the exception of the lower extremity arterial exam. If the difference in peak walking time (PWT) during the exercise tests between visits 1 and 2 was greater than 20%, participants were asked to complete a third exercise test, at least 72 hrs after visit 2. Once the variation in PWT was deemed acceptable (i.e. <20%), participants were assigned, using a randomized, crossover design, to undergo a single session of either HT or a control treatment (CON) prior to a symptom-limited cardiopulmonary treadmill exercise test. The primary study outcome was the difference in peak walking time (PWT) between HT and the CON conditions. Secondary outcomes included the differences between visits in claudication onset time (COT), blood pressure and calf muscle oxygenation at rest and during exercise, pulmonary oxygen uptake ($\dot{V}O_2$) and plasma ET-1, IL-6 and TNF-a concentrations post-treatment and post-exercise. Prior to the experimental visits, participants were asked to report to the laboratory in a fasted state (>8 hrs postprandial), refrain from exercise (24 hrs), smoking (>4 hrs), and take their usual medications.

Pulmonary function tests

Pulmonary function tests were performed following the American Thoracic Society and European Respiratory Society guidelines ¹. FVC and FEV1 were measured and reported as both raw and %predicted values ².

Symptom-limited cardiopulmonary exercise test

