Participants were instructed to ingest a core temperature sensor (CorTemp, HQ Inc., Palmetto, Florida, United States) the night before the experimental visits. Upon arrival, participants were allowed to rest for 15 min and were then instrumented with leg skin thermistors (MLT422; ADInstruments, Colorado Springs, CO, United States) and a blood pressure cuff on the upper arm that was connected to an automated monitor (Suntech CT40, Suntech Medical, Morrisville, North Carolina, United States). An intravenous catheter was placed in an antecubital vein of the left arm for blood sampling. After 30 min of rest in the semi-recumbent position, participants were fitted with liquid-circulating trousers as described previously ⁴. In the CON session, water at 33°C was circulated through the trousers for 90 min using a water pump (HTP-1500, Adroit Medical, Louden, Tennessee, United States). We have previously demonstrated that this regimen elevates skin temperature by approximately 2°C, but does not evoke measurable changes in core body temperature, heart rate and blood pressure ⁴. In the HT session, water at 43°C was circulated through the tube-lined trousers using a heated bath circulator (HT; Aqua Relief Systems, Akron, Ohio, United States) with the goal of increasing leg skin temperature to 37-38°C. The following parameters were assessed every 5 min during baseline and throughout the 90-min intervention: intestinal temperature (HQ Inc., Palmetto, Florida, United States), leg skin temperature, blood pressure, and heart rate. Prior to the onset of the treatment and at 45 and 90 min, patients were asked to subjectively grade thermal comfort scores using an 11-point feeling scale ⁵. After the completion of the treatment, participants were promptly escorted to an adjacent room and performed a symptom-limited exercise test as in visits 1 and 2. Blood samples were taken at baseline, at the end of the 90-min treatment and 10 min after the end of the exercise test.

Assessment of tissue oxygenation

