All data were analyzed using SAS v9.4. Data are presented as mean \pm SD. Variables assessed during exposure to HT or CON (blood pressure, intestinal temperature, HR, and skin temperature) were compared using a two-way repeated measures analysis of variance (ANOVA). PWT and COT times were compared using a paired t-test. All measurements taken at COT and PWT were time-aligned (isotime) between visits 3 and 4 at the point of the earlier COT and PWT. Blood pressure during exercise was compared between groups using a two-way repeated measures ANOVA. Missing values during the exercise test were imputed by linear interpolation, using the mean of the values from the two adjacent stages. If the value for the final stage was missing, then it was recorded as a repeat of the previous stage. TSI% and $\dot{V}O_2$ are represented using the mean of the final 20 seconds for each stage. Staged averages were compared using a two-way repeated measures ANOVA. When a group-by-time interaction was detected, post-hoc analysis compared values at each time point. A Bonferroni adjustment was applied to correct for multiple comparisons when appropriate.

REFERENCES:

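### Where HT and CON are compared at each 5-minute reading, Holm could replace Bonferroni: same family-wise error, never fewer time points declared

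*Combined protocol and SAP*

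**What the plan says.** Under Heat and control treatments: "The following parameters were assessed every 5 min during baseline and throughout the 90-min intervention". The parameters are intestinal temperature, leg skin temperature, blood pressure and heart rate.

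Under Statistical Analysis: "Variables assessed during exposure to HT or CON (blood pressure, intestinal temperature, HR, and skin temperature) were compared" by two-way repeated measures ANOVA. Later in the same paragraph: "When a group-by-time interaction was detected, post-hoc analysis compared values at each time point". The next sentence is the only one on multiplicity: "A Bonferroni adjustment was applied to correct for multiple comparisons when appropriate". It does not say which comparisons form a family or what the divisor is.

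Under Experimental Design, blood pressure at rest is among the secondary outcomes. The primary outcome lies elsewhere: "The primary study outcome was the difference in peak walking time (PWT) between HT and the CON conditions", tested by one paired t-test.

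The document states no sample size, significance level, SD, effect size or correlation between readings.

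**The concern.** Once the interaction is declared, HT and CON may be compared at 18 successive readings from the same people. Bonferroni tests each one at the same strict level, however many of the others have already been rejected. Holm relaxes the level after each rejection and keeps the same error guarantee, so some time points that Holm would declare are missed without any gain in protection.

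At stake is how the treatment-period curves are read. Resting blood pressure is a secondary outcome, and the temperature series show whether the intended heating was achieved. A steady difference that is flagged at only some readings may look as though it comes and goes. The matter is one of efficiency and clarity in non-primary variables; it does not bear on the trial's main conclusion.

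**Working it through.** The plan has no figure of its own to reproduce.

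**From the document.** Readings every 5 min for 90 min: 90/5 = 18 (19 with a time-zero reading; more if baseline readings are tested too). The comparisons are paired, because the design is a crossover.

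**Assumed.** Two-sided 0.05; 16 pairs; a maximum effect of 0.8 SD of the paired difference; a family of the 18 treatment readings; correlation between readings either exchangeable (0.5 to 0.85) or first-order autoregressive (0.5 to 0.95).

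**Thresholds.** Bonferroni tests every reading at 0.05/18 = 0.0028, a critical t of 3.57 on 15 df against 2.13 unadjusted. Holm orders the p-values and compares the i-th smallest with 0.05/(18 − i + 1), stopping at the first failure. The first step is 0.05/18 = 0.0028, the seventh 0.05/12 = 0.0042, the last 0.05. Two results follow without simulation:
- Every Holm threshold is at least as large as Bonferroni's, so Holm never declares fewer points.
- The first steps are identical, so the chance of at least one significant point is the same.

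**Power at one named reading (noncentral t, 16 pairs), unadjusted vs Bonferroni.**
- 0.5 SD: 0.47 vs 0.10
- 0.8 SD: 0.85 vs 0.40
- 1.2 SD: 0.99 vs 0.86
- 2.0 SD: 1.00 vs 1.00

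The cost of adjustment is large for moderate effects and vanishes for large ones.

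**Mean number of the 18 points declared (simulation).** For a plateau reached by 30 min, with exchangeable correlation 0.5, 0.7 and 0.85:
- Bonferroni: 5.67, 5.65, 5.57
- Holm: 7.04, 7.10, 7.02
- Ratio: 7.04/5.67 = 1.24; 7.10/5.65 = 1.26; 7.02/5.57 = 1.26

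A separate simulation gave 5.6-5.7 against 6.9-7.2, a gain of about 22-27%. For a linear ramp it gave 2.1 against 2.4-2.5, a gain of about 11-18% (percentages from unrounded counts). In absolute terms that is about 1.4 points for the plateau (for example 7.04 − 5.67 = 1.37) and 0.3 to 0.4 for the ramp. When only the last four readings carry the effect, per-point power is 0.39 against 0.40, so there is almost no gain.

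**Family-wise error with no effect anywhere.** 0.044, 0.040 and 0.022 at autoregressive correlation 0.5, 0.8 and 0.95. The figures are the same for both methods, since the first step is shared.

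**The case against.** Four objections deserve weight.

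1. A reader might infer that the treatment-period comparisons are badly underpowered. The documents do not support that: every input to a power calculation is missing. Over assumed inputs of 10 to 30 pairs and effects of 0.3 to 2.0 SD, Bonferroni power at one reading runs from 0.01 to 1.00. Skin temperature has an HT goal of 37-38°C against control water at 33°C; if that contrast is large relative to its SD, little is lost.

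2. A reader might also infer that no planned comparison pools the plateau readings. It does: with a within-participant error term, the ANOVA condition main effect is a paired comparison of each participant's mean over the readings entered. On the plateau above, with exchangeable correlation 0.5, 0.7 and 0.85, its power over 18 readings was 0.94, 0.87 and 0.79, against 0.97, 0.94 and 0.89 for a mean of the last six readings. Setting about 0.40 at one named reading against such figures compares different questions. What stands is narrower: the main effect is not named as the key test, and six baseline readings, if entered, would dilute it to 0.76, 0.63 and 0.54.

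3. The pointwise tests may not be reached. With a constant effect from the first reading, the Greenhouse-Geisser interaction test rejected only about 1-6% of the time, and then neither method is used. With a plateau by 30 min it rejected in 0.69, 0.96 and 1.00 of runs at the three correlations.

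4. The divisor of 18 is a reading of the text. The post-hoc sentence directly follows the one on exercise-stage averages, and the Bonferroni sentence leaves its scope open. This affects the size of the gain but not its direction: Holm never rejects less in any family, including the exercise stages.

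The argument that Bonferroni heavily overcorrects because neighbouring readings are alike is only partly right. The family-wise error falls well below 0.05 only at very high correlation, and the plan documents no correlation.

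**Conclusion.** The point holds as a free improvement to the post-hoc tests. That Holm keeps the error guarantee and never declares fewer points is exact and needs no assumption about the data. The size of the gain, about a quarter more time points for a plateau and 11-18% more for a ramp, rests on an assumed 16 pairs, 0.8 SD and a family of 18. It shrinks towards nothing for late or very large effects. The claim is not that these analyses are underpowered as planned, nor that they ignore the repeated readings. The primary test of peak walking time is untouched.

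**What to change.** Under Statistical Analysis, replace Bonferroni with Holm for the post-hoc time-point comparisons, and state that the family is the time points tested within each variable. Say explicitly whether this covers the treatment-period series, the exercise stages or both, and whether baseline readings are in the family.

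Optionally, add one supplementary analysis per treatment-period variable: the within-participant HT-CON difference in the mean of the last 30 minutes (six readings), with a 95% CI, using the same session's pre-treatment mean as a covariate or subtracted. Show the 5-minute curves descriptively beside it. The window and the baseline handling are judgement calls. For the plateau at 16 pairs and 0.8 SD, subtracting baseline lowered power from 0.95 to 0.74 at autoregressive correlation 0.8 and from 0.89 to 0.85 at 0.95, but raised it to about 1.00 under exchangeable correlation.

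The cost is wording and a re-run, with no new data. Holm does not come with simultaneous confidence intervals as simple as Bonferroni's, but the plan promises none at single time points. The section is written in the past tense. If results have already been seen, report the Holm results beside the Bonferroni ones and label any added contrast as post hoc.
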